STUDY PROTOCOL

Full project title: *Changes in outcomes of treatment for adolescent anorexia nervosa after implementation of Family Based Treatment in a Norwegian child and adolescent mental health service: A retrospective cohort study with prospective follow-up*

Short project title and acronym: *Akershus university hospital retrospective cohort study of family based treatment / ARCS-FBT*

Short Norwegian title for public communication: *Familiebehandling av anoreksi – effekt og erfaringer med innføring av FBT-modellen*

SUMMARY

A two-group retrospective exploratory cohort study with longitudinal follow-up comparing adolescents with anorexia nervosa treated with generic family therapy to those treated with the manualised Family Based Treatment (FBT). The primary aim is to investigate whether adoption of FBT has led to faster normalisation of weight and lower rates of eating disorder in early adulthood. Secondary aims are to investigate whether implementation of FBT has changed the time to discharge, heterogeneity of patient weight change across treatment, rates of adverse events, rates of readmission, patient experiences of the treatment, long term functional outcomes and mortality. Data are extracted from patient health records, reported by participants and extracted from public registries.

STUDY MANAGEMENT AND RESEARCH GROUP

This study will be conducted by the Department of child and adolescent mental health services at Akershus university hospital. Director of research and innovation, professor [name], is responsible for research at Akershus university hospital. Head of Department [name] has the administrative responsibility for the project on behalf of the hospital.

Project manager and principal investigator:

[name]

Clinical psychologist, Department of child and adolescent mental health services

Project group:

[name]

Consultant, Department of child and adolescent mental health services

[name]

Senior researcher, Department of research and development in mental health

[name], MPhil

Research coordinator, Department of child and adolescent mental health services

BACKGROUND

Adolescent anorexia nervosa is a severe eating disorder related to long-lasting morbidity and premature mortality (1, 2), and recent reports from hospitals suggests the prevalence in Norway may be increasing (3). The manualised family therapy “Family Based Treatment” (FBT) is currently the treatment approach for adolescent anorexia nervosa with the largest evidence base (4). FBT is recommended as a first line treatment in multiple service contexts (5, 6).

While there has been conducted several randomised controlled trials of FBT in academic settings (7), there are few large studies examining outcomes when FBT is implemented in clinical practice. A

systematic review published in 2015 found five such dissemination studies. Of these, three were conducted in academic clinical settings with the number of patients ranging from 11 to 20, and two were retrospective studies reporting changes in service use patterns after implementation of FBT in a regular mental health service (8). Two later studies have compared the outcomes achieved in clinical trials of FBT to those of FBT provided in regular clinical care, finding these to be comparable (9, 10), but these have both been conducted in highly specialised clinical contexts. More studies with higher power are needed to confirm the effectiveness of FBT when disseminated to regular healthcare contexts.

At the Child and Adolescent Mental Health Service (CAMHS) unit Nedre Romerike BUP, adolescent anorexia nervosa has consistently been treated with family therapy for about 20 years. In 2018 the unit implemented FBT, making several changes to the form of family therapy provided. As part of treatment monitoring, patients are weighed regularly, and weight data are recorded in patient health records.

Restrictive eating and corresponding weight loss are core features of anorexia nervosa, besides distorted views of the body and rigid preoccupation with losing weight and avoiding weight gain. Normalisation of eating behaviour and weight status is hence the primary treatment goal, making the patient health records in this case contain relevant outcome data.

The long-term course of anorexia nervosa is heterogeneous, and in some patients the disorder shows a protracted course, with long term morbidity and functional impairment, as well as increased mortality (11). There are few longitudinal studies of treatment outcomes with long follow-up periods (12). As Norway has a general system of personal identification numbers, following up patients across multiple public registries is a viable way to assess long term outcomes without the patients needing to participate in reporting.

AIMS

The primary aim is to assess the short and long-term effectiveness of FBT compared with non-manualised family therapy. This is operationalised as testing whether the adoption of FBT has led to patients achieving normalisation of weight faster than with the previously delivered family therapy, and whether it will lead to less treatment provided for eating disorders in adulthood. Secondary aims are to assess whether adoption of FBT have resulted in reduced time to discharge, changed the heterogeneity of weight gain across patients, whether there have been changes in the rates of adverse events and readmissions, and to assess whether the implementation of FBT has led to changes in long-term functional status and rate of mortality.

DESIGN AND METHODS

Participants and recruitment

This is a two-group retrospective exploratory cohort study with prospective longitudinal follow-up in public registries. Eligible participants are all patients initiating treatment during the years 2015-2020 with the eating disorder team at Nedre Romerike BUP with a primary ICD-10 diagnosis of F50.0 Anorexia nervosa or F50.1 Atypical anorexia nervosa. Patients will be excluded if they were treated during the years 2018-2020 and FBT was never initiated. It is estimated that the final sample size will be approximately 200.

Eligible participants will be identified through review of patient health records. Participants will be contacted by letter with information about the study, including a link to an online video explaining more about the study. Study personnel will make a follow-up telephone call approximately a week later to allow the eligible participant to ask any questions they may have before deciding on participation in the study. Participants who are interested in participating will be directed to a website

where they can sign an electronic consent form and complete a short survey about their experience of treatment. The consent form and treatment experience survey will be implemented in “Tjenester for Sensitive Data”, which has appropriate security and allows for verified electronic signatures.

Participants will be contacted after they have reached age 16, and thus are able to give informed consent. They will be encouraged to discuss participation with their parents or other legal guardians.

Endpoints and data collection

Primary endpoint for the retrospective study is weight restoration, defined by patients having a weight measurement placing them at or above 95% of expected body weight (50. percentile) for age given Norwegian population norms, following established definitions of weight restoration (10).

Secondary endpoints are discharge from treatment and readmission to treatment (the latter is assumed to be right-censored).

Adverse events will be defined as debut of suicidal ideation, attempted suicide, debut of self-harming behaviour, severe self-harm where medical attention is indicated, hospitalisation for low weight or medical complications from low weight, admission to inpatient treatment for anorexia nervosa, involuntary gastric tube feeding, parental separation, and initiation of contact with child protective services.

Participant experiences and satisfaction with services will be assessed using the Generic Short Patient Experiences Questionnaire (GS-PEQ) (13).

The primary endpoint for the prospective study is continued morbidity, defined as being currently in treatment in specialist health care for any eating disorder. Secondary endpoints are mortality, level of education and employment status.

Data for the retrospective part of the study will be extracted from electronic patient health records. Weight data will be extracted directly from the electronic patient health record system (DIPS). One researcher will further go manually through all records of included patients and extract dates of treatment start, adverse events, discharge and any readmission, as well as checking the record for any weight measurements recorded but not entered into the weight database. As covariates we will also extract age, sex, gender, family structure, extent of care benefits received during treatment (pleiepenging), and comorbid disorders (ICD-10 diagnoses). Another researcher will independently extract data from a random 10% subsample for control and reliability assessment of coding.

Each participant will be assigned a random case identity number, which will be used for identification in all dataset files when data is analysed. Participant national identity numbers will be stored along with the corresponding case identity number in a separate file, the identity key file. Access to the identity key file will be restricted to the project manager and researchers performing data extraction. It will also be delivered to the agencies maintaining the relevant public registries.

When extracted, data will be entered directly into a REDCap database maintained by Akershus university hospital. Access will be restricted to researchers in the project group. Data will be stored and analysed de-identified.

Data for the prospective part of the study will be acquired from the following public registries: Norwegian Patient Registry, Norwegian Cause of Death Registry, and the databases “Attachment to employment, education and welfare benefits” and “Educational attainment of the population” collated by Statistics Norway. Data will be acquired from these databases in three waves; five, ten and twenty years after the last participant initiated treatment. All registry data will be acquired, stored and analysed de-identified.

Analysis plan

Statistical analysis will be conducted in a Bayesian framework using the Stan platform through the R (14) package brms (15).

We will evaluate whether adoption of FBT has led to faster weight normalisation by fitting a parametric survival model to the number of days until weight restoration is achieved. We will also fit models with gender, age, baseline weight, comorbid disorders and family structure as covariates, and further investigate whether any of these act as moderators of FBT compared with previous treatment. Similar parametric survival models will also be used for modelling differences in time to discharge and readmission. Differences in the rate of adverse events will be modelled using Poisson regression.

We will also evaluate differences between the cohorts in treatment course by fitting multilevel spline models to weight data with knots for every 4 weeks in treatment. Weight measurements will be nested within patients, and patients nested within cohorts. Spline models will allow for modelling non-linear weight change over the course of treatment, and the multilevel structure at the patient level will allow us to evaluate changes in heterogeneity of treatment response pre and post adoption of FBT, as well as visualise trends and heterogeneity of weight change across the course of treatment.

Analysis of prospective data will use parametric survival models or logistic or ordinal regression models, depending on the level of time specificity available in the data.

We have conducted simulations to investigate statistical power, assessing the type S (sign) and type M (magnitude) error rates, given inference based on the posterior median. We made the assumption of achieving at least a sample size of 150 patients and that implementation of FBT has led to a 10% increase in the probability of an event (i. e. weight restoration or discharge). With 1000 simulations, we estimated a type S error of 0.00 and an M error of 0.89, suggesting a very low risk of estimating the sign of the effect incorrectly and a small risk of underestimating the effect size. We conclude that the study will be adequately powered to achieve its primary aim.

The analysis will employ weakly informative prior distributions, using previous studies and other external knowledge (for instance about the biological limits of weight gain per day) to construct priors that rule out impossible areas of the parameter space (17).

ETHICAL CONSIDERATIONS

This study does not involve any direct experimental manipulation, and as long as the process of extracting and analysing data from patient health records and public registries is conducted with due care, there is no risk of harm to the participants. FBT has been widely implemented in Norwegian health care based on findings from experimental studies in treatment settings quite different from regular public healthcare services. Research on the short and long-term effectiveness of FBT in a Norwegian context hence has considerable value to society and future patients receiving treatment for anorexia nervosa.

STUDY TIMELINE AND PLANS FOR DISSEMINATION

The study was approved with qualifications by the Regional Ethics Committee in 2021 with a requirement to adjust the protocol to seek informed consent from all participants or their legal guardians. Final approval was granted in July 2022. The process of identifying and contacting eligible participants will start as soon as approval is received.

Data extraction for the retrospective part of the study will start for each participant as soon as informed consent is obtained. It is expected to be finished at the latest in the fourth quarter of 2023, with reliability checking completed within 2023. Preparation of computer code for analysis will be done concurrently, and analysis will commence when data extraction is completed. Preparation of reports

for publication will be done during 2023 and early 2024. Findings will be submitted to international scientific journals specialising in eating disorders. Abbreviated reports of findings will also be prepared and submitted to the journals of relevant Norwegian professional associations.

For the prospective part of the study data will be extracted in four waves, when the participant last initiating treatment has reached the planned time for follow-up and registries are updated. An individual follow-up date will be calculated for each participant, to adjust for differences in when participants initiated treatment, and the closest relevant registry entry to that date will be extracted. The project group will consult with the agencies maintaining the registries to plan data extraction in detail. Findings from the prospective part of the study will be reported in international scientific journals as they become available.

DATA RETENTION

Documentation for the clinical study will be retained for five years after final study report/publication.

FUNDING AND CONFLICTS OF INTEREST

The study is fully funded by the Department of child and adolescent mental health services at Akershus university hospital, through time allocated for research for the researchers who are employed at the department. [name] works as a clinician treating eating disorders at the Nedre Romerike CAMHS unit, but has worked there before and after implementation of FBT, and does as such not have a conflict of interest relating to the results of this study. [name], [name] and [name] have no conflicts of interest.

DECLARATIONS AND POLICIES

Amendments to the research protocol

The research protocol may require to be amended during the conduct of a clinical study. Any amendment to the research protocol will be agreed upon between the representative for the research responsible institution and the principal investigator. The amendments will be approved by the ethics committee.

Deviations from the research protocol

The study will be performed in accordance with this research protocol. Any protocol deviations will be reviewed by the representative for the research responsible institution. All deviations will be reported to the appropriate regulatory bodies as required.

Statements of compliance

The study will be performed in accordance with the ethical requirements defined in the Declaration of Helsinki. The study will not commence until all written approvals have been obtained.

Publication policy

Upon study completion the results of this study will either be submitted for publication and/or posted in a publicly accessible database of clinical study results. The results of this study will also be submitted to the Ethics Committee according to national regulations. All personnel who have contributed significantly with the planning and performance of the study (Vancouver convention 1988) may be included in the list of authors.

REFERENCES

3. Befring ÅM. Flere unge sliter med spiseforstyrrelse under koronaen2021 06.09.21. Available from: <https://www.nrk.no/norge/1.15279412>.

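### No first-course condition, no index-episode rule and no record of earlier treatment, so the two cohorts may differ in previously treated patients and no planned model can adjust for it directly

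*Combined protocol and SAP*

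**What the plan says.** Participants and recruitment sets the entry rule: "Eligible participants are all patients initiating treatment during the years 2015-2020 with the eating disorder team", with a primary diagnosis of F50.0 or F50.1. The only stated exclusion is "Patients will be excluded if they were treated during the years 2018-2020 and FBT was never initiated". The Background section places the cohort boundary: "In 2018 the unit implemented FBT, making several changes to the form of family therapy provided". It also says that at this unit "adolescent anorexia nervosa has consistently been treated with family therapy for about 20 years".

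Under Endpoints and data collection, one researcher will read every included record and "extract dates of treatment start, adverse events, discharge and any readmission". The covariate list there reads "As covariates we will also extract age, sex, gender, family structure, extent of care benefits received during treatment (pleiepenging), and comorbid disorders". The Analysis plan evaluates the primary retrospective endpoint by "fitting a parametric survival model to the number of days until weight restoration is achieved" and continues: "We will also fit models with gender, age, baseline weight, comorbid disorders and family structure as covariates".

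Neither covariate list contains earlier eating-disorder treatment. No section says which start is the index when a patient has more than one, or how a patient treated in 2015-2017 who starts again in 2018-2020 is classified.

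**The concern.** The comparison is before against after, without randomisation, so it relies on the two cohorts being alike or on measuring how they differ. Treatment history is a basic prognostic variable, and the index start is time zero for every survival model in the plan. Both are left open.

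The unit was treating this disorder long before 2015, so patients with an earlier course can start again inside the window. Suppose each patient enters once, at the first start in the window. Someone first treated in 2014 who returns in 2016 is then an index case in the early cohort. Someone first treated in 2016 who returns in 2018 is already in the early cohort, and the return counts there as a readmission. A patient returning to this team can be an FBT index case only after a gap of more than three years. If returners also regain weight more slowly, part of any apparent FBT benefit would come from case mix. Discharge, readmission and continued morbidity could be affected in the same way.

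**Working it through.** **The plan's own figure.** The plan gives no figure on this point. Its one design calculation (type S 0.00, type M 0.89, at least 150 patients) cannot be rebuilt, because the baseline event rate, follow-up, distribution and priors are not given. Nothing below depends on it.

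**Step 1: which index rule does the text imply?** Three features point to one entry per patient at the first start in the window:
- Readmission is a right-censored endpoint with its own survival model. If the last start in the window were the index, no readmission inside the window could occur. If every start were an index, the same return would be both an outcome and a new case.
- Each participant gets a single study identifier.
- Study timeline and plans for dissemination computes one follow-up date per participant from when treatment began.

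This is an inference; no sentence states the rule.

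**Step 2: shares under that rule.** Assumptions, none from the documents: constant flow of new patients, return probability p = 0.1-0.3, one return per patient, exponential gap with mean m = 1-2 years. Returners first treated before 2015 enter at time t after 1 January 2015 at a rate proportional to p·exp(−t/m). Against three years of new patients per cohort:
- Early returners: E = p·m·(1 − exp(−3/m)); share f0 = E/(3 + E).
- FBT-period returners: L = p·m·(exp(−3/m) − exp(−6/m)); share f1 = L/(3 + L).

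Let h be the restoration rate of returners relative to new patients (assumed 0.5-0.7). With no true effect, the crude rate ratio is (1 − f1 + f1·h)/(1 − f0 + f0·h).

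| p, m | f0 (2015-2017) | f1 (2018-2020) | ratio, h = 0.7 | ratio, h = 0.5 |
|---|---|---|---|---|
| 0.1, 1 year | 0.095/3.095 = 3.1% | 0.005/3.005 = 0.2% | 1.009 | 1.015 |
| 0.2, 1.5 years | 0.259/3.259 = 8.0% | 0.035/3.035 = 1.2% | 1.021 | 1.035 |
| 0.3, 2 years | 0.466/3.466 = 13.4% | 0.104/3.104 = 3.4% | 1.032 | 1.054 |

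**Step 3: check by simulation of treatment episodes.** Assumptions: inflow from 2009, first course at about age 15, leaving the service at 18, return probability 10-30% after each course, mean gap 1.25-2 years. The spurious hazard ratio is taken as h^(f1 − f0).
- First start in the window as index: f0 about 3-11%, f1 about 0%. The ratio is 1.02-1.08 at h = 0.5, 1.01-1.04 at h = 0.7, 1.00 at h = 1 and 0.97-0.99 at h = 1.3.
- Every start, or the last start, as index: shares nearly equal, about 7-26% in each cohort; ratio about 1.00.
- Last start as index, with half of the returning patients in 2018-2020 not given FBT and so excluded: unequal again, for example 17% against 9%, with a ratio of 1.06 at h = 0.5.

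**Step 4: size against precision.** With an event in all 150 to 200 patients, the standard error of the log hazard ratio is 2/√150 = 0.16 to 2/√200 = 0.14. Since ln(1.05) = 0.049, a ratio of 1.05 is about a third of one standard error.

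**The case against.** The strongest reply is that the text can be read so that the asymmetry disappears. The protocol separates initiating treatment from readmission. If any return to the team is a readmission, a patient first treated in 2013 who comes back in 2015 is not eligible at all, just as a 2016 patient's return in 2018 is not a new entry. That reading is reasonable. It shows that the rule is ambiguous, but it does not supply the missing rule, and it leaves patients treated earlier by another service unaddressed.

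Other points also stand. No section says that previously treated patients regain weight more slowly. Background notes that some patients have a protracted course, which makes it plausible and no more. Adjustment for age, baseline weight and comorbidity may absorb part of any difference. There are opposing routes too: read literally, the exclusion removes 2015-2017 starters still in treatment in 2018-2020 without FBT. These are probably slow responders, and their loss would flatter the early cohort.

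A reader might therefore infer more than the documents support:
- *That relapsed patients do enter mainly the 2015-2017 cohort and the comparison does tilt towards FBT.* This needs both an unstated index rule and an undocumented slower recovery.
- *That the FBT cohort is almost purely new patients.* The three-year argument covers only earlier courses with this team; patients treated elsewhere can enter either cohort after any gap.
- *That the bias is about half the planned effect.* This sets a rate ratio beside a 10% rise in event probability whose scale is not stated. At an assumed 60% baseline, a relative 10% is a hazard ratio of ln(0.34)/ln(0.40) = 1.18, and ten points is ln(0.30)/ln(0.40) = 1.31. On the log scale, 1.05 is then about 30% or 18% of the effect.
- *That the bias in readmission is larger still.* Nothing in the documents allows a figure.

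**Conclusion.** The gap is established: there is no first-course condition, no index-episode rule, and no variable for earlier treatment in either the extraction or the models. The cohorts may therefore differ in their share of previously treated patients, and the planned adjustments could correct for that only indirectly.

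The direction and size are conditional. With first-start indexing and slower recovery in returners, the spurious ratio is about 1.01-1.05 in favour of FBT, about 1.02-1.035 in the central case, and at most about 1.08 in the simulation. If every start or the last start is the index it is about nil, unless returners are selectively not given FBT. If returners recover faster it reverses, to 0.97-0.99 at h = 1.3. All return rates, gaps and relative recovery rates are assumptions. The bias is modest beside the study's sampling error. It is still worth removing, because a larger sample would not reduce it and the remedy is cheap.

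**What to change.** 1. In Participants and recruitment, state that each patient enters once, at the first course started with the team in 2015-2020, and that later courses count only as readmission.
2. In Endpoints and data collection, add one item to the record extraction: eating-disorder treatment before the index course, with this team or elsewhere (yes/no).
3. In the Analysis plan, include that item in the adjusted models.
4. Report a sensitivity analysis limited to patients in their first course.

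The first step should not be taken alone: it fixes the index rule under which returners to this team gather in the early cohort, so the covariate has to come with it. If earlier treatment is correctly recorded and adjusted for, the spurious ratio from this source is 1.00. Making first-course patients the main population would also achieve this, but it changes the target group from all patients starting treatment, so it is better kept as a sensitivity analysis.

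The cost is one more extracted item in a review already planned for every included patient, and one more model parameter. No participants are lost from the main analysis. The limitation is that records of treatment given elsewhere may be incomplete.

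### Only the 2018-2020 cohort must have started FBT to be included, which can bias the comparison with 2015-2017 by an unknown amount in an unknown direction; the exclusion wording also needs aligning with the entry criterion

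*Combined protocol and SAP*

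**What the plan says.** Entry (Design and methods, Participants and recruitment) covers "all patients initiating treatment during the years 2015-2020 with the eating disorder team" with a primary diagnosis of anorexia nervosa or atypical anorexia nervosa. The next exclusion reads: "Patients will be excluded if they were treated during the years 2018-2020 and FBT was never initiated". No condition on the therapy begun applies to 2015-2017 starters. The Background says that at this unit "adolescent anorexia nervosa has consistently been treated with family therapy for about 20 years", but that is description, not an eligibility rule.

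The change is dated only by year: "In 2018 the unit implemented FBT, making several changes to the form of family therapy provided".

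The target of the comparison is worded in two ways. The Aims open with "The primary aim is to assess the short and long-term effectiveness of FBT compared with non-manualised family therapy", a contrast by therapy received, and the Summary describes the two groups in the same way. The Aims then operationalise this as "testing whether the adoption of FBT has led to patients achieving normalisation of weight faster than with the previously delivered family therapy", and the Summary likewise says "The primary aim is to investigate whether adoption of FBT has led to faster normalisation of weight".

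The Analysis plan fits a parametric survival model to days until weight restoration and nests patients within cohorts, but no section says how a patient is assigned to a cohort. The dates listed for manual extraction under Endpoints and data collection are treatment start, adverse events, discharge and readmission. FBT start is not listed.

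**The concern.** Starting FBT is an event at or after entry to treatment. Patients who left, were transferred, improved early or were judged unsuitable before FBT began disappear from the later cohort, while their counterparts in 2015-2017 stay in the comparator. If non-initiators differ in prognosis beyond the planned covariates (gender, age, baseline weight, comorbidity, family structure), time to weight restoration and time to discharge will differ between cohorts even if adoption did nothing.

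Prognosis need not differ for this to happen. If the clock runs from treatment start, and patients who restore before FBT begins never start it, those kept in the FBT cohort are by construction free of the event up to their FBT start.

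A smaller matter is wording. Entry is by the year treatment was initiated, but exclusion is by the year in which the patient was *treated*. A patient who started in 2017, was still in care in 2018 and never had FBT meets both the entry criterion and the literal exclusion. A 2017 starter who later moved to FBT is kept, but with no stated cohort.

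**Working it through.** The documents give no number of non-initiators, restoration rate, length of stay or delay to FBT, so every input below is an assumption unless its source is named. The plan has no figure of its own to reproduce on this point.

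**Step 1. Selection on prognosis, no true effect.** Initiators restore at a constant rate h = ln2/median, with median 6, 9 or 12 months. Non-initiators, a share q = 0.10 or 0.20 of starters, restore at k × h with k = 0.5, 1 or 2. Follow-up is cut at C = 12 or 24 months. Case mix is the same in both periods, so the comparator is a mixture of both types while the FBT cohort holds initiators only.

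Comparator rate = events / person-time = Σ w(1 − exp(−rC)) / Σ [w(1 − exp(−rC))/r], where r is h or kh and w is 1 − q or q. Apparent hazard ratio (FBT versus comparator) = h / comparator rate.

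- k = 0.5: 1.06 (median 12, C 12, q 0.10) to 1.17 (median 6, C 24, q 0.20)
- k = 1: 1.00 throughout
- k = 2: 0.86 (median 12, C 12, q 0.20) to 0.95 (median 6, C 24, q 0.10)

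Probability of restoration by 12 months, initiators versus all starters (q = 0.10 / 0.20):

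| Median | Initiators | All, k = 0.5 | All, k = 2 |
|---|---|---|---|
| 6 | 0.750 | 0.725 / 0.700 | 0.769 / 0.788 |
| 9 | 0.603 | 0.580 / 0.557 | 0.627 / 0.651 |
| 12 | 0.500 | 0.479 / 0.459 | 0.525 / 0.550 |

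The largest gap is 5.0 points in either direction (0.750 − 0.700; 0.500 − 0.550), or about 9% relative (0.500/0.459 = 1.09; 0.500/0.550 = 0.91). The power simulation in the Analysis plan assumes a 10% increase in event probability without saying whether that is absolute or relative. At the extremes, the artefact is therefore half of it (5.0/10 points) or about nine-tenths (9%/10%).

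**Step 2. Equal prognosis, delayed FBT start.** Everyone restores at rate h. FBT starts after an exponential delay of mean 0.5 to 2 months. Anyone restored first never starts it and is excluded. The clock runs from treatment start and C = 24 months. By simulation, the retained cohort's apparent rate is 0.83 of the truth (median 6, mean delay 2) to 0.96 (median 12, mean delay 0.5). The bias is against FBT.

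**Step 3. Literal reading of *treated*.** With uniform starts over the 36 months of 2015-2017 and exponential stay of mean m months, the share still in care on 1 January 2018 is (m/36)(1 − exp(−36/m)):

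- m = 9: 0.245
- m = 12: 0.317
- m = 18: 0.432

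If none of them had FBT, all are lost. If 90% moved to FBT, the loss is one-tenth of that: 2%, 3% or 4%. With all lost, the comparator's median stay falls from 6.2 to 4.6 months (m = 9), from 8.3 to 5.5 (m = 12) and from 12.5 to 6.7 (m = 18). If *treated* means initiating treatment, every figure in this step is zero.

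**Step 4. Undated implementation.** If FBT began on 1 January 2018, nothing is lost. Otherwise, early-2018 starters who never had FBT fall out of both cohorts: at most 1/36 = 2.8% of 2018-2020 starters per month of delay, with uniform starts.

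**The case against.** The strongest reply is that this is a deliberate comparison of therapies received. The Summary and the opening sentence of the Aims support it, and requiring FBT to have been started is the natural criterion for it. A reader might infer that the exclusion contradicts the study's aim; the documents do not support that. What stands against the reply is that the criterion is one-sided, and that the same sections also ask what adoption achieved. A cohort restricted to initiators does not answer that alone.

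A reader might also infer that a quarter or more of the comparator will be lost. That needs the literal reading of one word, assumed stays and nobody moving to FBT. The sentence follows directly on a criterion about initiating treatment and subdivides the same years, so a wording slip is much the likelier explanation. The missing implementation date and crossover rule are likewise mostly clarification. Leaving out early-2018 starters could serve as a transition gap and is not in itself a bias.

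Nor do the documents support saying that the effect of the exclusion could never be examined. Eligible patients are identified by record review, and applying the exclusion requires knowing whether FBT was started, so non-initiators can be counted at screening. Only their outcomes are out of reach, because extraction is limited to included patients and follows consent.

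Finally, Step 1 is hypothetical, includes a hazard ratio of 1.00 and models no covariate adjustment. That is fair. It shows what the rule could do, not what it has done.

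**Conclusion.** The point holds as a one-sided selection in the primary retrospective comparison that no other section offsets. The textual finding is firm; the size and direction of any bias are not known. Under the stated assumptions with no true effect, differing prognosis gives an apparent hazard ratio anywhere from 0.86 to 1.17, and delayed FBT start with equal prognosis gives an apparent rate of 0.83 to 0.96 of the truth, against FBT. It would be wrong to conclude that the plan favours FBT, or that bias is certain.

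The mismatch between *treated* and initiating treatment is a separate, lesser matter. It has no effect under the likelier reading and shortens comparator times under the literal one. The comparison remains usable, but cohort membership should be settled before analysis. This should be fixed.

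**What to change.** (a) In the exclusion, replace *treated* with initiating treatment.

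(b) State the date on which FBT was implemented and assign cohort by treatment start before or from that date. Earlier starters then stay in the comparator whatever happens later.

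(c) Invite 2018-2020 starters who never began FBT on the same terms as everyone else and extract their data. Report their number and the reasons. Add a by-period comparison of all starters beside the FBT-initiated one. The sponsor may keep the FBT-initiated comparison as primary.

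(d) Add FBT start date to the extraction list, so that earlier starters who moved to FBT can be counted and the FBT-initiated analysis can separate time before FBT.

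Requiring family treatment of some kind to have been started in both periods would not repair the asymmetry. It does not mirror the FBT condition, since 2018-2020 patients given only generic family therapy would then enter the FBT-period cohort.

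**Cost.** The protocol's own rules require ethics committee approval of the amendment. If the expected sample of about 200 splits evenly and 10-20% of later starters are non-initiators (assumptions), the extra patients analysed number 100 × q/(1 − q), or about 11 to 25. With 50-80% consenting (assumed), about 14 (11.1/0.8) to 50 (25/0.5) would be approached. The all-starters estimate will be diluted by non-initiators, by roughly their share if adoption did nothing for them, and also by earlier starters who later moved to FBT. That is why both comparisons should be shown.
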